 177 crossover study design of the study with the sequence of treatment nested within the
 178 patient, and this was the random effect. Breakfast meals were excluded from postprandial
 179 analysis if: 1) the rate of change was greater than 0.5mg/dL/min in the 1 hour prior to
 180 breakfast, 2) subjects gave a subsequent bolus prior to 120 minutes following the breakfast
 181 bolus, or 3) subjects deviated from their typical breakfast.

182 For the postprandial glucose analysis (Table 2) there were limited observations available,
 183 but the estimated average glucose excursion was less for hyaluronidase compared to
 184 standard weeks on Day 1 of infusion set life (12-24 hours after the first hyaluronidase
 185 infusion) and Day 3 of infusion set life (immediately after second hyaluronidase
 186 infusion). This effect was lost on Day 2 of infusion set life (36-48 hours after the first hyaluronidase
 187 infusion) and Day 4 of infusion set life (24 hours after the second hyaluronidase infusion).
 188 The study was not powered to show a difference in glucodynamic parameters, but Cmax
 189 and tmax tended to be lower immediately after hyaluronidase infusions. Postprandial
 190 profiles obtained from CGM glucose values are presented in mean ± standard error for
 191 meals analyzed on Days 1-4 of infusion set life in Figure 3. There were too few meals
 192 available for analysis beyond Day 4 of infusion set life to allow postprandial analysis.

193
 194
 195

Table 2: Postprandial glucodynamic parameters following hyaluronidase injection

[figure not shown]
	0 hours post Hyaluronidase		12-24 hours post Hyaluronidase		36-48 hours post Hyaluronidase	
	Standard (N=11)	Hyal (N=11)	Standard (N=14)	Hyal (N=10)	Standard (N=11)	Hyal (N=13)
Estimated glycemic excursion*	24.8	-6.7	20.7	-5.4	14	26.9
P-value	<0.001*		<0.001*		<0.001*	
Cmax°						
Mean ± SD	69.5 ± 47.4	43.5 ± 44.5	72.0 ± 48.8	36.9 ± 35.1	51.6 ± 32.0	56.4 ± 25.9
Median, IQR	63 (31,80)	34 (7,68)	77.5 (19,117)	29 (17,48)	46 (33,76)	52 (42,69)
P-value	0.296		0.167		0.681	
tmax‡						
Mean ± SD	84.5 ± 49.3	69.1 ± 67.2	92.9 ± 58.9	76.5 ± 55.8	65.4 ± 32.6	73.8 ± 40.2
Median, IQR	65 (50,105)	50 (10,240)	82.5 (60,130)	60 (45,120)	65 (50,95)	55 (45,90)
P-value	0.3		0.5		0.591	

196
 197 P-values were obtained using a mixed-effects model accounting for crossover study
 198 design of the study with the sequence of treatment nested within the patient, and
 199 this was the random effect.

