727 Withdrawal of a subject will be considered for the following reasons: 1) Failure to
728 monitor their sensor and infusion sites on a daily basis; 2) developing >1.0 mmol/L
729 ketones on 2 or more occasions and failing to change their infusion set or a single
730 episode of diabetic ketoacidosis due to an infusion site failure. For subjects who
731 withdraw or who are withdrawn, their data will be used for analysis purposes up until
732 the time of withdrawal.

733

734 **Confidentiality**

735 For security and confidentiality purposes, subjects will be assigned an identifier that
736 will be used instead of their name. De-identified subject information may also be
737 provided to Medtronic Diabetes.

738

739 **Level of Risk**

740 This research proposal in children is consistent with United States Department of
741 Health and Human Services, Protection of Human Subjects, Subpart D, Section
742 46.404 (Research not involving more than minimal risk).

743

744 **Planned Duration of the Entire Study**

745 Planned duration of the entire study will be 6 months.

747 **CHAPTER 6: STATISTICAL CONSIDERATIONS**

748

749 This is a pilot study to determine if there are any clinical issues with using Fiasp® in
750 the 670G hybrid closed-loop system. These studies are not statistically powered.

751

752 In the blinded cross-over studies (Part I) we will use data obtained during the
753 second week of each arm to compare the following measurements using a mixed-
754 effects model accounting for crossover study design of the study with the sequence
755 of treatment nested within the patient:

756

a) time in range (70-180 mg/dl)

757

b) percent time <70 mg/dl,

758

c) mean glucose,

759

d) glucose CV,

760

e) total daily insulin dose,

761

f) total daily basal insulin,

762

g) insulin delivery from MN to 6AM, and 6AM to MN

763

764 We will test to see if there is any difference in pharmacodynamics when using
765 Fiasp® in the home environment when they are eating their usual breakfast.

766

767 Insulin pharmacodynamics following the standard breakfast will be assessed by
768 measuring the peak glucose concentration (C_{max}), time to C_{max} (t_{max}), and estimated
769 average glucose excursions were assessed using sensor glucose values at a time
770 interval of 0 to 180 minutes after breakfast bolus. If a bolus was given between
771 120-180 minutes following the breakfast bolus, CGM values were only used up to

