772 the time of the bolus. The glucose at the time of the breakfast bolus (Time 0) will be
773 set to 0 mg/dL for each meal, and the remaining CGM values were adjusted
774 proportionally to allow analysis of postprandial glucodynamic parameters. We will
775 utilize a mixed-effects model accounting for crossover study design of the study with
776 the sequence of treatment nested within the patient. Breakfast meals are excluded
777 from postprandial analysis if: 1) the rate of change was greater than 0.3mg/dL/min
778 in the 1 hour prior to breakfast, 2) subjects gave a subsequent bolus prior to 120
779 minutes following the breakfast bolus, or 3) subjects deviated from their typical
780 breakfast. Dinner meals will be assessed when there has been no additional food
781 intake after dinner. The duration of insulin delivery to cover the meal will be
782 determined by the time it takes the post prandial glucose to reach 160 mg/dL
783 beyond 1 hour of eating. The peak glucose will also be recorded.

783

784 During the 6 week optimization study (Part II) we will use data obtained during the
785 first two weeks of the study (before data was reviewed and changes made by the
786 investigators) to data obtained during the last two weeks of the 3 month optimization
787 period. We will compare the following measurements using paired t-tests for data
788 with a normal distribution and a Mann-Whitney rank sum test for data that is not
789 normally distributed:

790

a) time in range (70-180 mg/dl)

791

b) percent time <70 mg/dl,

792

c) mean glucose,

- 793 d) glucose CV,
- 794 e) total daily insulin dose,
- 795 f) total daily basal insulin,
- 796 g) insulin delivery form MN to 6AM, and 6AM to MN
- 797 h) CHO:I ratios at breakfast, lunch and dinner
- 798 i) Active insulin time
- 799 j) Number of days between infusion set changes
- 800 k) Erythema (mm) and induration (mm) at infusion sites when they are changed
- 801 l) Average daily insulin, and mean glucose for each day of infusion set wear
- 802 m) Number of episodes of unexplained hyperglycemia in the first month vrs the
- 803 last month
- 804
- 805
- 806
- 807

808 **CHAPTER 7: REFERENCES**

809

- 810 1. Heise T, Hovellmann U, Nosek L, Sassenfeld B, Thomsen KMD, Haahr H.
811 Pharmacokinetic Properties of Fast-acting Insulin Aspart Administered in Different
812 Subcutaneous Injection Regions: Response to the commentary by Nuggehally R. Srinivas.
813 Clinical drug investigation 2017.

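### The breakfast model's only stated structural term reduces, read literally, to a patient intercept, so the three breakfasts on each insulin may be treated as more independent than they are

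*Combined protocol and SAP*

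**What the plan says.** Chapter 6 announces a test for the breakfast comparison: "We will test to see if there is any difference in pharmacodynamics when using" the new insulin at home. The parameters are Cmax, tmax and average glucose excursion. For the model, the plan will "utilize a mixed-effects model accounting for crossover study design of the study with" the term "the sequence of treatment nested within the patient. Breakfast meals are excluded". It lists no fixed effects, other random term, covariance structure or degrees-of-freedom method.

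Section 1.2.3 describes the same breakfast method in the earlier hyaluronidase study and states the role of the nested term: "patient, and this was the random effect. Breakfast meals were excluded from postprandial" analysis under its listed conditions. Chapter 6 does not repeat that label in its breakfast paragraph.

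Chapter 3 (Part 1 and the meal-testing procedure) randomises each participant to one of two sequences. It asks for the same breakfast on three days with each insulin, with one infusion-set change before the first test day. During the blinded phase staff avoid changing pump settings, except at the participant's request or for safety.

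The window is stated: sensor values from 0 to 180 minutes after the breakfast bolus. For a later bolus at "120-180 minutes following the breakfast bolus, CGM values were only used up to" that bolus, and a meal with a bolus before 120 minutes is excluded. The chapter also says of the pilot in "the 670G hybrid closed-loop system. These studies are not statistically powered".

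**The concern.** A sequence does not vary within a patient. Nesting it there gives one level per patient, which is the same grouping as patient alone. The design has a further level: three breakfasts belonging to one patient on one insulin. Those three share a week, a planned infusion-set change and any setting change made in that arm, and they do not share these with the three breakfasts on the other insulin. A patient intercept cannot absorb this correlation, so the model would count up to 120 breakfasts as independent given the patient.

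The treatment estimate is not biased by this. Its stated uncertainty is at stake: standard errors that are too small, and intervals and p-values that are too favourable for all three breakfast parameters.

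The weekly CGM and pump measures in Chapter 6 carry the same phrase. With one value per patient per arm a patient intercept is sufficient there, so this point does not extend to them.

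**Working it through.** The plan gives no power, alpha or SD figure to reproduce, so the check is structural and then conditional on assumed SDs.

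**Inputs.** From the documents: up to 20 patients in Part 1, 2 sequences, 2 insulins, 3 breakfasts per insulin. Assumed: all 20 enrolled, two-sided 5% test, no true difference, one value per breakfast, and the ratio r = patient-by-period SD / meal SD.

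**Step 1: levels of the random term (20 patients).**
- Patient: 20.
- Sequence within patient: 20, identical to patient.
- Period within patient: 40.

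**Step 2: what a patient-intercept model does.** There are 20 × 2 × 3 = 120 rows. After patients, period and treatment, the residual df are 120 − 20 − 1 − 1 = 98. Of these, 18 come from patient-by-period differences (20 − 2) and 80 from meals within a patient and period (40 × 2). In units of the meal variance:
- Mean square for meals: 1.
- Mean square for patient-by-period, which actually governs the treatment contrast: 1 + 3r².
- Pooled mean square that the model uses instead: [18(1 + 3r²) + 80] / 98.
- Factor by which the SE is too small: √[(1 + 3r²) / pooled].

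| r | Implied within-period correlation, r²/(1 + r²) | 1 + 3r² | Pooled | SE too small by | Type I error |
|---|---|---|---|---|---|
| 0 | 0 | 1.00 | 1.000 | 1.00 | about 5% |
| 0.4 | 0.14 | 1.48 | 1.088 | 1.17 | about 9% |
| 0.8 | 0.39 | 2.92 | 1.353 | 1.47 | about 18% |

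The result depends only on r, so it applies to excursion, Cmax and tmax alike, each with its own unknown r.

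**Step 3: separate simulation.** A balanced crossover with 20 patients, indexed by the correlation of one patient's meals within a period after removing the patient effect, gave 4.7%, 7.9%, 10.9%, 15.1% and 21.9% at correlations 0, 0.1, 0.2, 0.3 and 0.5. Analysis at the patient-by-period level (18 df) stayed between 4.8% and 4.9%. The two calculations agree.

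**Step 4: excluded breakfasts.** With meal SD 25 mg/dL and patient-by-period SD 0, 10 and 20 (r = 0, 0.4, 0.8), and each breakfast valid with probability 0.6, simulated type I error was 5%, 7% and 12%. Paired patient means gave 4–5%.

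**Step 5: cost of the paired analysis when r = 0.** The critical value is 2.10 on 18 df against 1.98 on 98 df. The unrounded ratio is 1.059, so the interval is about 6% wider. At 60% validity the chance of at least one valid breakfast on each insulin is (1 − 0.4³)² = 0.936² = 0.876, or about 17.5 of 20 patients.

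**Step 6: cut and full windows.** For assumed curves (peak 60 mg/dL at 60–90 minutes, −20 to +20 at 180 minutes) the 0–120 minute average exceeds the 0–180 minute average by 2.4 to 13.8 mg/dL. If 30% of meals on one insulin and 10% on the other were cut at 120 minutes, identical curves would differ by 0.2 × 2.4 = 0.5 to 0.2 × 13.8 = 2.8 mg/dL. This is an illustration only; the documents give neither curves nor cut rates.

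**The case against.** **The phrase may mean something else.** Because sequence is constant within a patient, the authors may have meant treatment order, that is, period within patient, in a model described as accounting for the crossover. That is the term recommended here. Chapter 6 also does not itself call the phrase the random effect. This stands: the wording is ambiguous rather than demonstrably wrong. But an analyst following it literally would fit only a patient intercept.

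**The shared variation may be small.** Breakfast, carbohydrate amount, bolus timing and preset ratio are held constant, and setting changes are discouraged. Its size is unknown, and at zero there is no inflation. This stands too, and is why a range is shown.

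**It is an unpowered pilot with no alpha, primary endpoint or decision rule.** That limits the consequence. It excuses wide intervals, but not intervals that are too narrow in a comparison the plan says it will test.

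**Stronger readings that the documents do not support.**
- Because "average glucose excursions were assessed using sensor glucose values at a time" interval, a reader might infer that individual CGM readings are the model rows, with far greater inflation. That needs two unfavourable readings at once: readings as rows, and a patient intercept only. Cmax and tmax are one value per meal by nature, and time zero is set meal by meal, so one value per breakfast is the natural reading, though not explicit.
- A reader might take the very small excursion p-values in Table 2 of section 1.2.3 as evidence that readings were treated as independent in the earlier study. The table prints no excursion SD and concerns another study, so it settles nothing.
- A reader might say the averaging window is unspecified. It is specified, including the cut; only the comparability of cut and full meals is left open.

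**Conclusion.** The point holds as a specification fault that should be fixed. Taken literally, the stated structure omits patient-by-period variation in a design with three breakfasts per patient per insulin. Whenever that variation exists, intervals and p-values for the breakfast parameters are too favourable. The size is conditional: with 20 patients, all breakfasts valid and one value per breakfast, SEs are too small by 1.00, 1.17 and 1.47 times at assumed SD ratios of 0, 0.4 and 0.8. With 60% of breakfasts valid the type I error at the largest ratio falls from about 18% to 12%. If the authors meant period within patient, the model is already adequate and only the wording needs correcting. The consequence is overstated precision in one planned pilot comparison, not a wrong sample size or a wrong trial decision.

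**What to change.** In Chapter 6, state that each valid breakfast contributes one value each for average excursion, Cmax and tmax. Replace the nesting phrase with one of:

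1. patient-by-insulin means, compared as paired values with a period effect; or
2. fixed treatment, period and sequence, with random patient and random patient-by-period effects and small-sample degrees of freedom (for example Kenward-Roger).

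Keep the stated 0–180 minute window with its cut. Add a 0–120 minute average as a sensitivity analysis: every included meal has it, because one exclusion is that, "in the 1 hour prior to breakfast, 2) subjects gave a subsequent bolus prior to 120" minutes. It should not replace the main window, since it misses the late part of the excursion. Say also how Cmax and tmax are taken from cut meals.

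The cost is wording only, with no new data or procedures. If there is no patient-by-period variation, the paired interval is about 6% wider; otherwise intervals widen as they should. Option 1 weights a patient with one valid breakfast the same as a patient with three, and drops patients with none on one insulin. Option 2 keeps them.

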200 *AUC=Area under the Curve (mg/dL)

201 °Cmax=Peak glucose concentration (mg/dL)
202 ‡Tmax=Time to peak glucose concentration (minutes)
203 *represents statistical significance (i.e. P<0.05)
204

205 **Figure 1-5:** Postprandial glucose profiles by Day of infusion set wear (and hours
206 following hyaluronidase infusion)

207
208
209

210 **1.3 Study Overview**

211

212 *Use of Fiasp®:* Fiasp® insulin has been approved for sale in the USA, and has been
213 available since February 7th 2018. Although it is not approved for pumps, it will be used in
214 pumps off-label because of it has a more rapid onset of action. The 670G closed-loop
215 system automatically adjusts basal rates throughout the day and night to minimize hyper
216 and hypoglycemia. Use of the 670G provides a unique opportunity to assess how Fiasp®
217 works in a closed-loop system and to determine if any changes need to be made to the
218 670G pump to optimize the use of Fiasp®.

219

220 According to the FDA guidelines we do not think this study requires an IND since we meet
221 all of the following six conditions:

- 222 i. it is not intended to be reported to FDA in support of a new indication for use or to
223 support any other significant change in the labeling for the drug;
- 224 ii. it is not intended to support a significant change in the advertising for the product;
- 225 iii. it does not involve a route of administration (it is still being given subcutaneously) or
226 dosage level, use in a subject population, or other factor that significantly increases
227 the risks (or decreases the acceptability of the risks) associated with the use of the
228 drug product;
- 229 iv. it is conducted in compliance with the requirements for IRB review and informed
230 consent [21 CFR parts 56 and 50, respectively];
- 231 v. it is conducted in compliance with the requirements concerning the promotion and
232 sale of drugs [21 CFR 312.7]; and
- 233 vi. it does not intend to invoke 21 CFR 50.24.”

234

235

236 **1.4 Protocol Synopsis:**

237

238 This is a pilot outpatient study conducted at Stanford to obtain preliminary data on
239 how Fiasp® works in a closed-loop system. The plan will be to enroll up to 20
240 subjects for each part of the study. Part 1 is a blinded cross-over study to assess
241 how well Fiasp® insulin works when used with the 670G pump compared to aspart
242 insulin and will take 6 weeks for a subject to complete. Part 2 is a Fiasp®

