461 more than 10 mm of erythema or induration. They will be given a ruler for making
462 these measurements. If there is more than 3 mm of induration or redness they will
463 be asked to take a picture and enter these measurements into a text to the study

464 coordinator or submit the information directly into RedCap.

465

466 The goal will be to have sensor wear at least 80% of the time and in automode at
467 least 70% of the time. The pump will be uploaded to a research Carelink account
468 each week. While in the blinded phase of the study the clinical staff will refrain from
469 making changes to 670G pump settings unless requested by the subject or for
470 safety reasons such as an episode of severe hypoglycemia (unconsciousness or
471 seizure), >10% time <70 mg/dl, or >20% of the time over 250 mg/dl.

472

473 **Part 1: Randomized, cross-over, blinded study to assess any adaptations of**
474 **the 670G pump to Fiasp® and to assess meal pharmacodynamics of Fiasp®**
475 **compared to aspart with a typical breakfast in the home environment**

476

477 Participants will have a 2 week run-in on their usual home insulin (aspart of Fiasp®).
478 During the run-in, their pump will be downloaded weekly, reviewed by the clinical
479 staff and adjustments will be made to their settings as needed to optimize their
480 glycemic control. Participants will then be randomly assigned to 2 sequences of
481 testing starting with either aspart or Fiasp®. They will use each insulin for two
482 weeks. The participants and the investigators will be blinded to the insulin. During
483 the second week of using a blinded insulin they will have the meal
484 pharmacodynamics testing. They will then cross-over to the other insulin and
485 during the second week they will repeat meal pharmacodynamics testing. At the
486 end of each week they will upload their 670G pump to a Carelink clinical (research)
487 account and it will be reviewed by the research staff for safety purposes.

488

489 Procedure for meal testing. For each week of meal testing they will be asked to
490 have 3 days with a consistent breakfast that is the same for all 6 days they are
491 doing a meal test (3 days on each insulin). The breakfast studies should ideally
492 occur on standard work days (not holidays or weekends). On these three days they
493 will be asked to have a dinner with at least 30 grams of fat and no additional food in

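### Dinner duration and peak are scored on absolute glucose with no account of glucose at the start of dinner, so recovery from a high start is counted as meal response

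*Combined protocol and SAP*

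**What the plan says.** Chapter 6 (Statistical Considerations, Part 1) gives two dinner outcomes. The duration of insulin delivery to cover the meal is "determined by the time it takes the post prandial glucose to reach 160 mg/dL" "beyond 1 hour of eating. The peak glucose will also be recorded". The only stated condition for using a dinner concerns later eating: "Dinner meals will be assessed when there has been no additional food" intake afterwards. For dinner there is no subtraction of a starting value, no covariate for it, no rule on pre-meal trend and no rule on later boluses.

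Breakfast, in the same paragraph, is handled differently. "The glucose at the time of the breakfast bolus (Time 0) will be" set to zero and later sensor values are adjusted to it. A breakfast is dropped if "the rate of change was greater than 0.3mg/dL/min" in the preceding hour, or if a further bolus came before 120 minutes. Chapter 3 (Part 1) also drops mornings on which a correction dose was needed.

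On the size of the dataset, section 1.4 states "The plan will be to enroll up to 20" subjects for each part. Chapter 3 sets three test days per insulin, on which participants "will be asked to have a dinner with at least 30 grams of fat and no additional food in" the evening. Chapter 6 states that the studies are not powered.

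**The concern.** The duration outcome is meant to describe how long insulin takes to cover the meal. With a fixed 160 mg/dL line it also depends on where glucose stood when the meal began. Take a dinner that starts at 200 mg/dL and raises glucose hardly at all. Glucose must still fall 200 - 160 = 40 mg/dL before the duration ends, and the post-dinner peak will be near 200 mg/dL. Scored as breakfast is scored, the same trace would show almost no excursion.

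Dinner is also the less controlled of the two meals. It follows a free-living day rather than a closed-loop night, and its composition is fixed only by a minimum fat content. Chapter 3 argues for control at breakfast from overnight insulin delivery, bolus timing and identical carbohydrate. It makes no such argument for dinner.

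Two things are at stake. Variation in starting glucose adds noise to both dinner outcomes, with at most three dinners per insulin in up to 20 subjects. Also, dinners fall in the second week on the assigned insulin. If that insulin shifts late-afternoon glucose, the shift enters the dinner contrast and cannot be told apart from a different response to the high-fat meal.

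**Working it through.** **Inputs.** Table 1 (section 1.2.2), three-month 670G data: mean glucose 150.8 mg/dL, within-day CV 30.8%, 3.3% of values below 70 mg/dL, 24.5% above 180 mg/dL. The documents give no numerical glucose value at dinner. The 24-hour profile (Figure 1-4) is not shown in the text available. The all-day distribution is therefore used as a proxy, which is an assumption, and it is varied in step 4.

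**Step 1: spread.** SD = 0.308 × 150.8 = 46.4 mg/dL. For a lognormal with the same mean and CV, σ² = ln(1 + 0.308²) = 0.0906, σ = 0.301, and μ = ln(150.8) - σ²/2 = 4.971.

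**Step 2: reproduce the stated share above 180 mg/dL.**
- Normal: 1 - Φ((180 - 150.8)/46.4) = 26.5%.
- Lognormal: 1 - Φ((ln 180 - 4.971)/0.301) = 23.0%.

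These bracket the stated 24.5%, each within 2 points, so either shape is adequate for reading off 160 mg/dL.

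**Step 3: share above 160 mg/dL.**
- Normal, mean and CV: 1 - Φ(9.2/46.4) = 42.1%.
- Lognormal, mean and CV: 36.4%.
- Normal fitted to the mean and the 24.5% tail (SD 42.3): 41.4%.
- Normal fitted to both stated tails (mean 150.0, SD 43.5): 40.9%.
- Lognormal fitted to both stated tails: 35.4%.

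The range is 35-42%. Without any distributional shape, at least 24.5% of all-day values exceed 160 mg/dL, since every value above 180 does.

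**Step 4: sensitivity to the dinner-time mean, CV held at 30.8%.**

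| Mean at start of dinner (mg/dL) | Lognormal | Normal |
|---|---|---|
| 130 | 20% | 23% |
| 140 | 28% | 32% |
| 145 | 32% | 37% |
| 150.8 | 36% | 42% |
| 160 | 44% | 50% |

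The share drops below one third once the dinner-time mean is under about 147 mg/dL (lognormal) or 141 mg/dL (normal), which is only 4-10 mg/dL below the all-day mean.

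**Step 5: counts.** At full enrolment there are 20 × 6 = 120 dinners. The two mean-and-CV models give 120 × 0.364 = 44 to 120 × 0.421 = 51 starting above the threshold. The 20-50% range gives 24 to 60.

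**Step 6: dinners that the rule does not score.** The text does not say what duration to assign when glucose never exceeds 160 mg/dL, when it is already below 160 mg/dL at one hour, or when it does not return to 160 mg/dL overnight. Starting glucose affects which of these occurs: from 130 mg/dL, a rise of less than 160 - 130 = 30 mg/dL never reaches the line.

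**The case against.** **The percentage does not describe dinner.** A reader might infer from Table 1 that more than a third of dinners start above 160 mg/dL. The documents do not support that. The figures are all-day values and include post-meal peaks. Table 1 pools adolescents and adults, while this trial enrols from age 18, and adults had more time in range (73.8% against 67.2% in adolescents, section 1.2.2). Subjects also have two weeks of settings optimisation first. This stands: the share is a proxy with a wide range. The defect in the rule does not depend on the exact share.

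**The contrast need not be biased.** A reader might infer that the Fiasp-aspart comparison is biased. Chance differences in starting glucose balance in expectation in a randomised crossover, and stable differences between subjects cancel. What remains is noise, plus any real effect of the assigned insulin on pre-dinner glucose. That effect belongs to the insulin but is not a meal response.

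**Adjustment changes the question.** Starting glucose in week two is measured after randomisation. Adjusting for it estimates the meal response given the start, not the total effect of the insulin on evening glucose. This stands, and it is why both results should be shown.

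**Dinner is descriptive.** Dinner is absent from the list of Part 1 measurements for the mixed model, section 1.4 speaks of glucose levels after a high-fat meal, and the study is an unpowered pilot. An absolute peak is defensible for describing levels. A duration said to be that of covering the meal is harder to defend on an absolute scale, and a small sample makes avoidable noise more costly.

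**The gain in precision cannot be sized.** The documents give no SD for the rise after a high-fat dinner and no correlation between start and rise. Table 2 concerns breakfasts in a different study. No percentage reduction in variance should be claimed.

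**Conclusion.** The concern holds as a flaw in the scoring rule. As written, the dinner duration and peak partly measure the glucose at which dinner began, and the plan already applies the remedy to breakfast. The practical cost is added noise in both dinner outcomes, and a contrast that cannot separate a shift in pre-dinner glucose from the response to the meal.

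On the all-day proxy, about 35-42% of dinners would start above the threshold. For a dinner-time mean of 130-160 mg/dL at the Table 1 CV, the range is roughly 20-50%. This rests on Table 1 applying to the trial's adults and on a normal or lognormal shape. It does not establish a share for actual dinners or a bias of any given size. A covariate alone would also not be a complete repair, because time to 160 mg/dL is undefined or incomplete for some dinners.

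**What to change.** In Chapter 6, before unblinding:

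- Express dinner peak and mean excursion as change from sensor glucose at the dinner bolus, as for breakfast, over a window stated in advance. Compare the insulins with the same crossover mixed model.
- Keep absolute peak and time to 160 mg/dL. Report each unadjusted and again with starting glucose as a covariate. State that the start value is measured after randomisation, so the adjusted result is the meal response given the start.
- Treat dinners that do not return to 160 mg/dL as censored at a stated time, and use a method for repeated censored times within subject.
- State how dinners that never exceed 160 mg/dL, or are already below it at one hour, are scored.
- Report by insulin the number and share of dinners starting above 160 mg/dL.

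The cost is a few more lines of analysis plan and programming, and a second estimate to interpret for each absolute outcome. The starting value is already on the sensor trace, so no new data, visits or procedures are needed.
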